2.8.2. Secondary End-Points

Secondary end-points are: a.) treatment-related effects on anti-HSP70 concentrations, b.) forced vital capacities, c.) incidences of acute IPF exacerbations, d.) survival durations, e.) hospitalization rates, and f.) adverse event-rates.

- a.) Anti-HSP70 IgG concentrations- We have found anti-HSP70 is ONE OF MANY autoantibodies present in IPF patients, and it happens too to be ONE OF SEVERAL associated with IPF progression (14). Thus, we will be able to test for effects of rituximab on both global autoantibody production (Primary Endpoint), as well as its effects on a particular, clinically-associated specific autoantibody (anti-HSP70), pretreatment and 1,3,6 and 9 months post-treatment. Anti-HSP70 IgG will be measured by ELISA, as detailed in citation #14.
- **b.)** Forced vital capacities (FVC) by spirometry- In addition to FVC, other pulmonary function variables that are not formal endpoints (FEV $_1$, DL $_{CO}$, and O $_2$ requirement at rest and with walking), 6 minute walk distance, and Borg Dyspnea Assessments will be routinely measured pretreatment and at 1,3,6, and 9 months thereafter. These tests are standard operating procedures (SOP) for care of IPF patients at our centers.
- **c.)** Acute exacerbation frequencies- IPF patients typically experience slowly progressive, if somewhat episodic, lung function deterioration. Nonetheless, a sizeable proportion, variously estimated as 10-to-50% or more, develop acute exacerbations that can result in very rapid onset respiratory failure and death within days (4). Results of studies indicate that autoantibodies are involved in acute exacerbations of IPF. It is hoped that rituximab therapy will decrease the frequency or delay onset of acute exacerbations. Acute exacerbations will be defined by

participating physicians using current consensus criteria, i.e., worsening hypoxemia and dyspnea within the preceding 30 days, characteristic new radiographic pulmonary infiltrates, and no other evident cause of lung dysfunction after thorough clinical assessments (4).

- **d.)** Survival- Given the high mortality of IPF patients, efficacy of the experimental therapy could result in prolonged survival among treated subjects. Survival durations from study enrollment will be tabulated as both absolute survival and transplant-free survival.

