2.9 DATA AND POWER ANALYSES

2.9.1 Power Analyses:

Given the initial nature of this trial, definitive power calculations are speculative. Nonetheless, even moderate efficacy of the experimental treatment (as we anticipate) will produce evidence of same. Assuming a type 1 error rate of 0.05, a two-sided alternative hypothesis, n = 29/arm, and very conservative event rates (i.e., reduction of autoantibody titers in 33% of the experimental arm subjects, and 3% reduction in placebo controls) there is 80% power to detect a statistically significant effect.

The sample size of 58 for this clinical trial is based on exposing a minimum number of patients to potential risks of the experimental treatment, while still obtaining useful information. Analyses will follow intention to treat principles. Missing data techniques (e.g., multiple imputation) will be employed for subjects lost to follow-up, had transplants, or those who died. A sensitivity analysis will also be conducted in which transplantations and deaths will be considered failures.

2.9.2 Data Analyses:

Data analyses begin by describing baseline demographic and medical characteristics of the cohorts. Descriptive statistics, including measures of central tendency and dispersion, will be computed for continuous data (e.g., age). Frequency distributions will be estimated for categorical data (e.g., gender). To ensure balanced random assignments, treatments are examined in relationship to demographic and medical characteristics using the appropriate parametric (e.g., t-test) or nonparametric test (e.g., chi-square, Wilcoxon tests). Reduction of autoantibody titers from baseline to the nine-month follow-up visit will be calculated as a binary indicator (yes/no). A Fisher's Exact test will be used to compare rates of autoantibody titer reductions between the two groups. To control for the stratification variables, an exact logistic regression model will be used, including main effect for treatment and the stratification variables. Unbalanced baseline characteristics will also be included in the regression model.

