Linear regression models will be used to assess the treatment effect on continuous variable secondary endpoints. Main effects will include treatment, the stratification variables, and unbalanced baseline characteristics. Both the proportion of individuals with AEs and the count of AEs per person will be compared by treatment. A logistic regression model will be used to compare the proportion of subjects with acute exacerbations, hospitalizations, or adverse events (AEs) by treatment group, with main effects as described above. A negative binomial model will be used to evaluate the average count of AEs per subject by treatment group. For all models, the model assumptions (e.g., normality of residuals, over dispersion) will be investigated. If the assumptions are violated, transformations will be investigated. If adequate transformations cannot be identified, nonparametric approaches will be utilized. Small cell sizes may exist and exact methods may need to be employed.

Additional exploratory analyses will be conducted. This may include the use of mixed-effects regression models to examine the longitudinal course of the outcomes as well as survival analyses (e.g., Kaplan-Meier curves, log-rank test, Cox proportional hazards models) to evaluate time to event outcomes, such as time to death.

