2.10 ANTICIPATED RESULTS AND PITFALLS

2.10.1. Primary Endpoint:

By analogy to other rituximab-treated disease populations (29-39) we hypothesize the experimental treatment will result in reductions of autoantibodies. We are less certain of the time-to onset, magnitude, and duration of these effects in IPF patients, which is a primary goal of this trial.

We do not expect technical pitfalls, being very proficient with the anti-HEp-2 assays. To clarify, however, we are using these assays to detect nonspecific patterns that are not diagnostic for SLE, scleroderma, etc. (see Fig. 4 and citation 14). IPF patients with classic ANA tests diagnostic for SLE or other known autoimmune disorders will not be eligible for enrollment.

Findings herein of early autoantibody reappearances (e.g., within <6 months) would indicate that sequential, repeated rituximab dosing might be necessary in later definitive trials to test for clinical efficacy in IPF patients, or perhaps even warrant considerations for addition of a second agent (e.g., belimumab).

2.10.2. Secondary Endpoints:

We are proficient with ELISA and do not anticipate technical problems with the anti-HSP70 assays. We are able to reproducibly measure anti-HSP70 in all IPF plasma specimens, even when concentrations are <<mean normal values, and anticipate having serial, quantitative assay measures in all subjects. We expect rituximab will result in anti-HSP70 reductions, compared to controls, but pharmacodynamics of the effects remain to be determined.

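### FVC and anti-HSP70 are measured at five visits, but the committed linear regression names no outcome form, analysis visit or own-baseline adjustment, and the model that would use all visits is only optional

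*Combined protocol and SAP*

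**What the plan says.** Section 2.8.2 lists anti-HSP70 and FVC among the secondary endpoints. Both are measured at five time points; for FVC and the other lung function tests the wording is "will be routinely measured pretreatment and at 1,3,6, and 9 months thereafter". The summary of monitoring procedures (Table 2) and Appendix A agree.

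For the analysis, section 2.9.2 states: "Linear regression models will be used to assess the treatment effect on continuous variable secondary endpoints". The terms are treatment, the stratification variables and baseline characteristics found to be unbalanced. There is no visit, treatment-by-visit or subject term. Month 9 is fixed as the analysis time point for the primary endpoint only (2.8.1 and 2.9.2). Longitudinal models appear once, under additional exploratory analyses: "This may include the use of mixed-effects regression models to examine the longitudinal course of the outcomes".

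Section 2.9.1 adds that missing-data techniques, with multiple imputation as the example, will be used for subjects who are lost, transplanted or die.

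Section 1.1 gives the trial's goal as the magnitude and duration of autoantibody reduction. Section 2.10.1 says that onset, magnitude and duration are uncertain and that learning them is a main goal. Of anti-HSP70, section 2.10.2 says: "pharmacodynamics of the effects remain to be determined".

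**The concern.** The one committed sentence fits several different analyses: the raw month-9 value, change from baseline, month 9 adjusted for baseline, a separate regression at each visit, or a regression on each subject's slope or mean. They differ in what they estimate and in how precisely. If the choice is not fixed beforehand, it can be made after the data are seen.

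Two things are at stake.

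- **Anti-HSP70.** The primary endpoint is a yes/no result at month 9, so anti-HSP70 is the only continuous antibody measure among the formal endpoints and the one best able to show onset and loss of effect. The committed model has no term that estimates either.
- **FVC.** Differences between people in lung size are large relative to change over nine months. Precision therefore depends heavily on whether the subject's own baseline is used, and the plan brings it in only if it happens to be unbalanced.

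**Working it through.** **The plan's own figures.** The plan gives no power, variance or within-subject correlation for FVC or anti-HSP70. Its one power statement concerns the primary endpoint: "reduction of autoantibody titers in 33% of the experimental arm subjects, and 3% reduction in placebo controls", and "there is 80% power to detect a statistically significant effect". Exact enumeration of the two-sided Fisher test at 29 per arm gives 81.0%, so that figure reproduces. It does not bear on this point.

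**Step 1. FVC inputs, all assumed.** Subject intercept SD 0.7 L; slope SD s = 0.15 to 0.30 L/yr, independent of the intercept; residual SD r = 0.12 to 0.15 L; complete data. Visit times in years are t = 0, 1/12, 0.25, 0.5 and 0.75.

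**Step 2. Month-9 analyses, variance per subject.**

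- Raw month 9: V9 = 0.49 + 0.5625s² + r²
- Baseline: V0 = 0.49 + r², with covariance 0.49 between baseline and month 9
- Baseline-adjusted month 9: V9 − 0.49²/V0

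Example with s = 0.15 and r = 0.12: V9 = 0.49 + 0.0127 + 0.0144 = 0.5171, and V0 = 0.5044. The adjusted variance is 0.5171 − 0.2401/0.5044 = 0.0411.

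**Step 3. Slope model on all five visits.** The covariance matrix is V = 0.49·11′ + s²·tt′ + r²·I, with a common baseline mean and one slope per arm. The variance of the difference in 9-month change, 0.75(βA − βB), comes from the inverse of the summed information X′V⁻¹X. It is put on the same per-subject scale as step 2.

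| s | r | Adjusted month 9 | Slope model | Slope / adjusted | Raw month 9 | Raw / adjusted |
|---|---|---|---|---|---|---|
| 0.15 | 0.12 | 0.0411 | 0.0338 | 0.82 | 0.517 | 12.6 |
| 0.15 | 0.15 | 0.0567 | 0.0455 | 0.80 | 0.525 | 9.3 |
| 0.30 | 0.12 | 0.0790 | 0.0718 | 0.91 | 0.555 | 7.0 |
| 0.30 | 0.15 | 0.0946 | 0.0835 | 0.88 | 0.563 | 6.0 |

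The slope model is worth 1/0.91 − 1 = 10% to 1/0.80 − 1 = 25% more subjects than baseline-adjusted month 9.

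**Step 4. Two other readings of the same sentence.**

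- Change from baseline has variance 0.5625s² + 2r². In the first row this is 0.0127 + 0.0288 = 0.0415, almost the adjusted 0.0411. The 6-to-13-fold loss therefore applies only to raw month-9 FVC.
- A regression on each subject's least-squares slope has variance 0.5625(s² + r²/0.3806), where 0.3806 is the sum of squared deviations of the visit times. In the first row this is 0.5625(0.0225 + 0.0378) = 0.0339, or 0.83 of adjusted month 9. Over all four rows the ratio is 0.81 to 0.91.

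**Step 5. Type I error.** With one record per subject, simulation at 29 per arm with three binary covariates gives 5.1% at nominal 5%. If four post-treatment visits were stacked as independent rows, the design effect would be 1 + 3ρ and the true error 2[1 − Φ(1.96/√(1 + 3ρ))]:

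- ρ = 0.1: √1.3 = 1.140, error 8.6%
- ρ = 0.5: √2.5 = 1.581, error 21.5%
- ρ = 0.8: √3.4 = 1.844, error 28.8% (simulated 29.9%)
- ρ = 0.95: √3.85 = 1.962, error 31.8%

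**The case against.** The strongest reply is that nothing here is invalid. Every other confirmatory model in section 2.9.2 uses one record per subject: a yes/no titre reduction, the proportion of subjects with an event, a count of events per subject. The natural reading is one value per subject for these endpoints too, and that holds the error rate. They are unpowered secondary endpoints in an early-phase trial, and section 2.10.2 itself treats an FVC effect as speculative. Mixed models are at least mentioned. A regression on per-subject slopes fits the committed wording and, with complete data, captures nearly all of the FVC gain. All of this stands, and it makes the point one of specification and efficiency.

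Three stronger readings are tempting and are not supported:

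- **That type I error is inflated to about 29%.** The plan nowhere says that visits will be pooled. Even if they were, 29% needs a correlation of about 0.8 with four visits, and the documents give no correlation. The honest statement is a conditional range of about 9% to 32%.
- **That the only alternatives are pooling visits or discarding three of them.** Separate regressions by visit and per-subject slopes or means also fit the text.
- **That a subject who misses month 9 contributes nothing.** Section 2.9.1 commits to missing-data techniques, so at least part of that information could be recovered.

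The reply does not remove the gap itself. The outcome form, visit and baseline adjustment are unstated, and the time course has no committed analysis.

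**Conclusion.** The point holds as a gap in specification with a cheap improvement available. Section 2.9.2 does not fix what is analysed for FVC and anti-HSP70, at which visit, or whether the outcome's own baseline is in the model.

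For anti-HSP70 the cost is mainly the time course: a month-9 regression cannot show onset or duration. A model by visit would add little precision at month 9 itself when the data are complete.

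For FVC the cost is precision. The slope model has about 0.80 to 0.91 of the variance of baseline-adjusted month 9, and an unadjusted month-9 value has about 6 to 13 times that variance. Both ranges rest on the assumed SDs, on complete data and, for the slope model, on roughly linear decline. Other SDs would move them.

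The natural single-visit reading keeps type I error at nominal. The primary endpoint and its Fisher test are not affected.

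**What to change.** In section 2.9.2, make a repeated-measures mixed model the committed analysis for both endpoints, using all visits, the outcome's baseline value and the stratification variables.

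- **Anti-HSP70:** visit as a category with treatment-by-visit terms, and the baseline value as a covariate. Report months 1, 3, 6 and 9, with month 9 as the lead contrast.
- **FVC:** random intercept and slope on all five visits. Baseline enters as the first outcome with a common mean across arms, so it is not also a covariate. Report the treatment difference in 9-month change.
- **Missing data:** state how these models fit with the multiple imputation in section 2.9.1, including for subjects who die or are transplanted.
- **Sensitivity:** keep linear regression of the month-9 value adjusted for the outcome's own baseline.

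The cost is analysis-plan wording and slightly more programming, with no new data or visits. The downside is the linearity assumption for FVC, which the retained month-9 analysis checks.

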Study Objectives:	The primary goal of this multicenter, randomized, double-blind, Phase II clinical trial is to determine effects of rituximab on selected relevant immunological parameters of IPF patients, in comparison to effects of placebo alone. We anticipate the findings of this will lead to larger incremental trial(s) to definitively establish the clinical efficacy of this treatment.				
Study Hypothesis:	Our central hypothesis is that antibody-mediated autoimmunity can play an important role in IPF. We propose to begin to test our central hypothesis by establishing the efficacy and duration of autoantibody reductions by rituximab in IPF patients.				
Study Aims:	 To conduct a proof-of-concept, mechanistically-driven trial to reduce autoantibodies against HEp-2 cells. To determine the effects of the experimental treatment (rituximab), compared to placebo therapy, on secondary endpoints of: 1.) anti-heat shock protein 70 (HSP70) concentrations; 2.) changes in forced vital capacities; 3.) acute IPF exacerbation incidences; 4.) survival; 5.) hospitalization rates; and 6.) adverse event-rates. 				
Study Design:	 Following screening assessments, IPF patients who meet all inclusion/exclusion criteria will be randomly assigned to receive one of the following treatments in a ratio of 1:1: Arm A (n=29) - Rituximab Treatment: Premedications, consisting of 100 mg methylprednisolone I.V., and P.O. acetaminophen and diphenhydramine, will be followed by rituximab 1 g. I.V. Arm B (n=29) - Placebo Treatment: 				

	receive the premedication regimen (above), and placebo infusions of dextrose 5% in water (D5W), in lieu of rituximab, that are indistinguishable from the rituximab unit doses. Both treatments (premedications + either rituximab or D5W will be repeated 14 days after the first treatments. Patients will be monitored carefully for occurrence of adverse events, and changes in vital signs. Patients will be followed for a total of 9 months after their first study treatments.				
Planned Sample Size:	A total of 58 subjects will be enrolled in this multi-center trial from 5 participating medical centers				
Duration of Study:	Nine months				

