2.4 RANDOMIZATION

Following a determination of eligibility, subjects will be randomly assigned to one of two treatment arms (1:1 ratio), after stratification on the basis of gender, disease severity (DLCO <35% of predicted values), and current use of either/both pirfenidone and/or nintedanib. These stratifications will ensure ~equal proportions of severely ill patients, and ~equal proportions of males, in each arm. Male IPF patients have worse prognoses than females (1-4). Randomization assignments will be made in random block sizes of 2 and 4.

Randomizations will occur on the day of initial treatment, to reduce the possibility of "wasting" a randomization on a patient who fails to return for treatment.

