2.8 STUDY ENDPOINTS

2.8.1. The Primary End-Point

The primary end-point is reduction of autoantibody titers to HEp-2 cells, using indirect immunofluorescence (IFA), from baseline to the nine-month assessment point.

HEp-2 Autoantibody Titers: IFA methods to detect and quantify autoantibodies have been detailed by us previously (10,14). In brief, commercially available HEp-2 slide wells are incubated with titered dilutions of subject plasma (i.e., at 1:20, 1:40, 1:80, etc). After washing, the bound autoantibodies are detected with the secondary mAb (FITC-conjugated anti-human IgG). IPF specimens will be scored as positive if fluorescence intensity at titers ≥1:20 is greater than that of concurrent normal plasma specimens (determined by imaging in a fluorescent microscope) (14).

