- **e.) Hospitalizations** Indirect evidence of treatment efficacy could also be discerned by reductions of subsequent needs for hospital admissions. The frequencies and durations of hospitalizations among trial subjects will be tabulated and analyzed.
- **f.) AE Monitoring-** The National Cancer Institute Common Toxicity Criteria Scale will be used to define grades (severity) of AE and toxicities. An AE is defined as any untoward medical occurrence in a subject, regardless of its relationship to these treatments. Toxicity is an AE with a direct relationship to the study drug. All toxicities are AE, but not all AE are toxicities.

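### The linear models for FVC and anti-HSP70 use the outcome's own baseline as a covariate only if a balance check flags it; always including it would be a free gain in precision on two secondary endpoints, of a size the documents do not fix

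*Combined protocol and SAP*

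**What the plan says.** Section 2.9.2 (Data Analyses) assigns linear regression to the continuous secondary endpoints and gives one covariate rule: "Main effects will include treatment, the stratification variables, and unbalanced baseline characteristics". Imbalance is judged by arm comparisons described earlier in that section: "To ensure balanced random assignments, treatments are examined in relationship to demographic and medical characteristics". No threshold is given, and the characteristics are not listed.

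Section 2.4 (Randomization) describes "stratification on the basis of gender, disease severity (DLCO <35% of predicted values"), together with current antifibrotic use. Neither FVC nor anti-HSP70 is a stratum.

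Section 2.8.2 schedules anti-HSP70 "pretreatment and 1,3,6 and 9 months post-treatment". FVC and the other lung-function measures "will be routinely measured pretreatment and at 1,3,6, and 9 months thereafter".

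The response itself is not fixed. The aims in the synopsis speak of "changes in forced vital capacities", whereas section 2.8.2 lists only the capacities and the antibody concentrations. Section 2.9.2 names no visit or scale for these models. The primary endpoint, by contrast, runs "from baseline to the nine-month assessment point".

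**The concern.** Adjusting for an outcome's own baseline improves precision because baseline predicts follow-up, whether or not the arms differ at baseline. A rule that admits it only after a balance test flags it gives up that gain in most trials. Under randomization, a test at level p flags a given characteristic in a fraction p of trials. If own baseline is not among the characteristics compared, it is never a covariate.

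At stake is the precision of two secondary comparisons in a trial of 58. Section 2.10.2 hopes that an effect on lung function might be seen even in a cohort this small. The values needed are already being collected.

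**Working it through.** **The plan's own figure.** Section 2.9.1 states 80% power for the primary endpoint (33% v 3%, 29 per arm, two-sided 0.05). Exact enumeration of Fisher's test gives 81.0%, so that figure is reproduced, and nothing below changes it. No power is stated for FVC or anti-HSP70.

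**Inputs.** From the documents: 29 per arm, three stratification variables, and the covariate rule. Two-sided 0.05 is carried over from the primary power statement. Assumed, because the documents give neither: the baseline-to-follow-up correlation r (0.5 to 0.9) and an effect of 0.5 SD, where SD is that of the raw value.

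**Formulas.** With the raw-value variance set to 1, the residual variance v is:
- raw follow-up value, no baseline term: v = 1
- change from baseline, no baseline term: v = 2(1-r)
- own baseline as covariate: v = 1-r²

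The ratio of the third to the second is (1-r²)/[2(1-r)] = (1+r)/2. Power comes from the non-central t distribution with non-centrality 0.5/√(2v/29), on 58-2-3 = 53 degrees of freedom without baseline and 52 with it. For example, at r = 0.5 the non-centrality is 0.5/√(2×1/29) = 1.90 for change and 0.5/√(2×0.75/29) = 2.20 with baseline.

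| r | v, change | v, adjusted | ratio | power, change | power, adjusted |
|---|---|---|---|---|---|
| 0.5 | 1.0 | 0.75 | 0.75 | 46.4% | 57.8% |
| 0.7 | 0.6 | 0.51 | 0.85 | 67.5% | 74.4% |
| 0.8 | 0.4 | 0.36 | 0.90 | 84.0% | 87.6% |
| 0.9 | 0.2 | 0.19 | 0.95 | 98.7% | 99.0% |

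**Simulating the rule.** The settings were 40,000 trials each, with bivariate normal data, no missing values and three balanced, non-prognostic binary strata in every model. Own baseline was added only if its t-test fell below the threshold, and no other characteristic could enter. It was flagged in 4.8-5.2% of trials at p<0.05 and 19.6-20.5% at p<0.20.

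Change from baseline, 0.5 SD:

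| r | rule, p<0.05 | rule, p<0.20 | always adjusted | gain (points) |
|---|---|---|---|---|
| 0.5 | 46.5% | 47.7% | 57.0% | 9.3-10.5 |
| 0.7 | 67.7% | 68.7% | 73.5% | 4.8-5.8 |
| 0.8 | 84.1% | 84.7% | 86.7% | 2.0-2.6 |
| 0.9 | 98.7% | 98.8% | 98.9% | 0.1-0.2 |

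At 0.2 SD the gain is 1-3 points throughout. At 0.8 SD it is 5-7 points at r = 0.5 and at most 1.2 from r = 0.7 upward.

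The simulated variance ratio against unadjusted change is 0.764, 0.867, 0.918 and 0.969. Dividing 58 by these gives 75.9, 66.9, 63.2 and 59.9, the precision of about 18, 9, 5 and 2 more patients. The excess over theory (0.764/0.75 = 1.019) is the roughly 2% cost of chance baseline imbalance.

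**Raw follow-up value, 0.5 SD.** The rule gives 46.3-47.7%, 46.9-50.7%, 48.0-53.3% and 49.1-56.2% at the same four r. Always adjusting gives the same powers as in the table above, because with baseline in the model, absolute change and follow-up value yield the same treatment estimate and p-value. The gains are therefore about 9-11, 23-27, 33-39 and 43-50 points.

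**Type I error.** It is 3.7-4.9% under the rule for change, 1.3-4.3% for raw values, and 4.9-5.1% when always adjusting.

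**The case against.** The strongest reply is that the benefit cannot be sized from the documents. They give no correlation, SD, effect size, flagging threshold or response scale. On the change reading, which the synopsis wording supports for FVC, the gain almost vanishes at r = 0.9. The largest change-score gains need both r near 0.5 and a moderate to large effect. Sections 2.9.1 and 2.10.2 themselves call power, and the effect on FVC, speculative. All of this stands, and it limits the claim to a conditional one.

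A reader might infer that baseline information is thrown away. The documents do not support that: if change is analysed, every subject's baseline already enters through the response, and only its use as a covariate is missing. The exploratory mixed models could also use the pretreatment value, but section 2.9.2 makes them optional, so they do not close the gap.

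The simulation is also simpler than the plan. Section 2.4 treats sex and DLCO as prognostic, but the simulated strata are not. In the raw-value reading, prognostic strata would recover part of the loss. Other flagged lung-function measures could act as partial proxies. The raw-value gains are therefore upper-end figures.

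Finally, one might go on to argue for dropping the adjustment for unbalanced characteristics. Nothing calculated here supports that, and adding own baseline does not require it.

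**Conclusion.** The point holds as a free improvement on two secondary endpoints. The covariate rule does not secure the outcome's own baseline, and nothing else in the plan does so. If change is analysed, with 29 per arm and an effect of 0.5 SD of the raw value, always adjusting is worth about 9-11, 5-6, 2-3 and 0.2 points of power at r = 0.5, 0.7, 0.8 and 0.9. The variance ratios are about 0.76, 0.87, 0.92 and 0.97. If raw follow-up values are analysed the gain is larger, less whatever prognostic strata recover. The reading of the text is firm; the size rests on the assumed r, effect, threshold and response scale.

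A reader might take this as a validity problem. It is not: the present rule is conservative rather than inflated under the null, and the primary test, its power and N = 58 are unaffected.

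**What to change.** In section 2.9.2, state that the linear models for FVC and anti-HSP70 always include the baseline value of that outcome, on the same scale as the response and transformed in the same way if a transformation is used. This is in addition to treatment, the stratification variables and any unbalanced baseline characteristics already planned.

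In the same sentence name the response and visit, for example absolute change from baseline to month 9, which matches the primary endpoint's visit. The scale must be stated because percent change and log values, unlike absolute change, do not give the same result as the follow-up value.

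Add that the logistic models, which refer back to this covariate list, keep their present covariates, since exacerbations, hospitalizations and adverse events have no baseline value. Leave the rule on unbalanced characteristics, the primary model, the imputation plan and the exploratory mixed models as written.

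The cost is wording, one degree of freedom per model and about 2% extra variance from chance baseline imbalance, which the simulated gains already include. No new data are needed.
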